Aim 2. Test the hypothesized electrophysiological mechanism and rule out a placebo effect as cause for the symptomatic benefit, using randomized allocation of rhythmic stimulation to a control condition, namely random (not rhythmic) stimulation.

Aim 3. Gather additional preliminary information for a future clinical efficacy trial and NIH grant application. This information will include (a) the duration of effect after the end of stimulation, which is crucial information for designing chronic treatment, and (b) preliminary information on individual

characteristics that predict improvement with simulation, e.g. demographics, tic severity, premonitory urges, sensory hypersensitivity, ADHD, tic suppression ability, and tic phenomenology.

Completion of these Aims will give a clear go/no-go signal for a future clinical trial of chronic MNS delivered by a portable, wristwatch-style device.

STUDY DESIGN

Overall study timeline

The study will complete enrollment within 11 months and complete all human subjects procedures within 1 year.

Overview of each subject's participation

First we screen potential participants to ensure they meet criteria for study enrollment, and characterize their symptoms and other demographic and clinical features. They then participate in 2 stimulation sessions, at least a week apart, which are identical except that one session uses rhythmic and one uses arrhythmic MNS with the same number of total pulses per minute. Session order is randomized and participants are blinded to order. (Biological carryover effects are very unlikely.) Tics before, during and after stimulation epochs are video recorded for later analysis blind to time, stimulation (on *vs.* off), and stimulation type (rhythmic *vs.* arrhythmic).

Recruitment

Sources may include clinical referrals, online advertising, and word of mouth. We will also involve the local chapter of the Tourette Association of America, which is a key part of our TAA Center of Excellence

Prior to first visit

1. REDCap presents an informed consent document to parents of potential child participants explaining the study, risks and benefits of participation and that participation is voluntary. The ICD will be provided online prior to the in-person visit. Adult participants will provide their own informed consent. For child participants, consent from one parent or guardian is sufficient, as the study is minimal risk. Children must assent to participate.

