You may experience one or more of the risks indicated below from being in this study. In addition to these, there may be other unknown risks, or risks that we did not anticipate, associated with being in this study. You will be told of any new information that may affect your willingness to participate in this study. [name] will answer any questions you have about these risks.

MNS

Likely:

- Discomfort in the forearm, wrist or hand during active stimulation
- Mild skin irritation from applying or removing the surface electrodes

Other study procedures

Likely:

- The questionnaires and interview may be slightly boring, fatiguing or challenging.
- The video recordings may be slightly boring

Rare:

- The questions that you are asked during this study could make you feel uncomfortable. If any question makes you feel uncomfortable, you may choose not to answer it.
- Confidential information about you may be accidentally disclosed. However, we think the risk of accidental disclosure is small. The information we gather during the course of the study is coded only by a study number and is kept separately from your name, address, etc.

LOCATIONS / SITES OF STUDY

Data collection: Washington University in St. Louis

Data analysis: Washington University in St. Louis

STUDY DURATION

Anticipated duration of entire research activity per participant:

- 2-4* days, usually over the course of 1-2 weeks

* Planned participation includes a screening visit followed by two stimulation sessions, the first of which may occur on the same day as the first stimulation session. The maximum of 4 days rather than 3 allows one additional make-up MNS session for each participant in the event of technical problems that prevent completion of the procedures.

Anticipated duration of entire research activity:

One year

SAMPLE SIZE

N = 32 (study completers)

Power considerations

We can estimate variance from the Nottingham tic frequency results. Fig. 5 in ref. [6] shows the SD of the improvement in tic frequency between the MNS on and off conditions to be ~81 (total tics per condition). The mean difference between conditions was ~41, corresponding to a nearly 30% mean decrease in tic frequency. A 25% decrease in tic severity using the YGTSS Total Tic Score (TTS) is highly predictive of *clinically meaningful* clinical improvement [17], and the TTS is highly correlated to tic frequency on video recordings [18,19].

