From these data, a sample size of 32 will have 81% power to find a statistically significant result for Aim 1 (two tails) assuming the population mean response is the 30% reported by our colleagues in Nottingham. This sample size provides 75% power to detect clinically meaningful (-25%) improvement (one tailed).

Estimating screen failures and dropouts at a total rate of 27%, we will plan to enroll up to 44 participants to arrive at 32 who complete the entire study.

INCLUSION CRITERIA

Inclusion criteria for all subjects:

- Age 15-64 inclusive at initial screening visit
- Informed consent by adult subject; assent by child and informed consent by guardian
- Current DSM-5 Tourette's Disorder or Persistent (Chronic) Tic Disorder
- At least 1 tic per minute (average) during the first 5-min. baseline video session on the first visit (as scored during the session by the investigator)

EXCLUSION CRITERIA

Exclusion criteria for all subjects:

- Unable to complete study procedures for any reason
- Has an implanted device that could be affected by electrical current
- Pregnancy known to participant or (for children) to the parent
- Known or suspected primary genetic syndrome (e.g. Down syndrome, Fragile X)
- Intellectual disability (known, or likely from history and examination)
- Head trauma with loss of consciousness for more than 5 minutes
- Significant neurologic disease, not counting TS (exceptions include febrile seizures or uncomplicated migraine)
- Severe or unstable systemic illness
- Factors (such as exaggerated signs) that in the judgment of the principal investigator make the video recording or YGTSS an inaccurate assessment of tic severity
- Judged by investigator to be unlikely to complete study procedures or to return for later visits
- Change in somatic or psychotherapeutic treatment in the 2 weeks preceding the first stimulation visit
- Planned change in somatic or psychotherapeutic treatment between the 2 stimulation visits

CONCOMITANT MEDICATIONS

Required: none

PROHIBITED MEDICATIONS

none

TREATMENTS AND DOSAGE

Rhythmic

- 10 Hz for 1-minute epochs (to replicate **Current Biology** report)

- 12 Hz for 5-minute epochs

Arrhythmic

- Same number of pulses per minute as in the rhythmic condition, but with a random inter-pulse interval, as implemented by the Nottingham group in the **Current Biology** report

Both

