An expert rater blind to condition and time point assesses the number of tics per minute. Change in tic frequency from baseline (stimulation off) is compared between 5-minute MNS-on epochs on the rhythmic vs. the arrhythmic day. Subjects who do not complete both stimulation visits will not be included in this analysis. A repeated measures ANOVA will be used to compare effects of visit, order (rhythmic day first or second) and stimulation (on vs. off) on tic frequency. The hypothesized change is a significant interaction of visit, order and stimulation factors ($p \leq 0.05$),

showing greater improvement (off to on) with rhythmic vs. arrhythmic stimulation. This analysis includes the first six 5-minute blocks on each MNS day (i.e., the blocks that all participants complete).

[Time Frame: During rhythmic MNS stimulation]

4. Change in tic severity during rhythmic MNS (vs. arrhythmic MNS)

Overall tic severity for each 5-minute block is rated once on a 5-point scale by an expert blind to condition and time point. The scale is the Intensity item from the Yale Global Tic Severity Scale [YGTSS], which uses integer scores from 0 (no tics) to 5 (severe intensity). For this analysis, we will define tic severity as $\max\{\text{phonic tic intensity score, motor tic intensity score}\}$. Change in tic severity from baseline (stimulation off) is compared between 5-minute MNS-on epochs on the rhythmic vs. the arrhythmic day. Subjects who do not complete both stimulation visits will not be included in this analysis. A repeated measures ANOVA will be used to compare effects of visit, order (rhythmic day first or second) and stimulation (on vs. off) on tic frequency and severity. The hypothesized change is a significant interaction of visit, order and stimulation factors ($p\le.05$), showing greater improvement (off to on) with rhythmic vs. arrhythmic stimulation. This analysis includes the first six 5-minute blocks on each MNS day (i.e., the blocks that all participants complete).

[Time Frame: During rhythmic MNS stimulation]

Secondary Outcome Measures:

5. Change in tic severity after MNS ends

Duration of benefit will be estimated as follows. A repeated measures ANOVA will compare the change in tic frequency from baseline, during each 1-minute-long period following the end of stimulation. Here baseline means the tic frequency during the last 5 minutes of MNS from the same day.

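### Aim 2 drops everyone without both visits: a modest loss of information, and a possible bias if loss after visit 1 differs by session order

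*Combined protocol and SAP*

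**What the plan says.** Primary Outcome Measures 3 (frequency) and 4 (severity), and the Aim 2 paragraph under Data analysis, share one rule: "Subjects who do not complete both stimulation visits will not be included in this analysis". The method is the same in each, with frequency or severity as the response: "A repeated measures ANOVA will be used to compare effects of visit, order (rhythmic day first or second) and stimulation (on vs. off) on tic" (cut before the named outcome). The hypothesis is "a significant interaction of visit, order and stimulation factors", meaning a larger off-to-on improvement with rhythmic than with arrhythmic stimulation.

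Outcomes 3 and 4 specify the data used: "This analysis includes the first six 5-minute blocks on each MNS day". From steps 7 and 12 of the Stimulation protocol, these are four off blocks (baseline included) and two on blocks at each visit. The design overview adds: "Session order is randomized and participants are blinded to order".

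On losses, Power considerations says only: "Estimating screen failures and dropouts at a total rate of 27%, we will plan to enroll up to 44 participants", so as to reach 32 completers. Screen failures and drop-outs are not separated. The plan describes no missing-data assumption, no sensitivity analysis for incomplete participants and no report of drop-out by order.

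**The concern.** In an ordinary crossover, someone seen once adds little because differences in level between people dominate. Here the compared quantity is a change within a visit, so each person's tic level is already removed. A visit-1-only participant therefore carries some information on rhythmic versus arrhythmic stimulation, through comparison with people who had the other type first.

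The second question is comparability. Sessions are at least a week apart, and the plan lists discomfort during stimulation as likely. Whether someone returns may depend on what happened at visit 1. If rhythmic stimulation works better, as Aim 2 hypothesises, visit-1 benefit differs by order and so may the losses. Enrolling up to 44 protects the number of completers but not their comparability. Aim 2 is the randomised test of whether the benefit is specific to rhythmic stimulation, and the Objectives tie completion of the Aims to a go/no-go decision on a later trial.

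**Working it through.** **1. The plan's own figures (Power considerations).** The plan reports "the SD of the improvement in tic frequency between the MNS on and off conditions to be ~81" tics and says: "The mean difference between conditions was ~41, corresponding to a nearly 30% mean decrease in tic frequency". The standardised effect is d = 41/81 = 0.506. With n = 32, a two-sided paired t test at 0.05 has power 79.2% (81.7% by normal approximation), against 81% stated. For a 25% decrease, d = 0.506 × 25/30 = 0.422 and one-sided power is about 75%, as stated. Enrolment is 32/(1 − 0.27) = 43.8, so 44. The figures reproduce, but the 81% is for Aim 1 and both rest on the on/off contrast. No power is given for Aim 2.

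**2. Information lost.** Let D1 and D2 be a participant's off-to-on improvement at visits 1 and 2, with common SD σ and correlation ρ. Take n completers and m visit-1-only participants, split evenly by order. In the full visit × order × stimulation model, the variance of mean(D1) − mean(D2) within an order is proportional to:

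- completers only: 2(1 − ρ)/n
- all visit-1 data used: (1 − ρ)²/(n + m) + (1 − ρ²)/n

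The proportional reduction is (1 − ρ)/2 × m/(n + m). The documents do not give ρ or m. The ceiling is m = 44 − 32 = 12, if every loss came after a completed visit 1.

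| ρ | m = 6 (6/38 = 0.158) | m = 12 (12/44 = 0.273) |
|---|---|---|
| 0 | 7.9% | 13.6% |
| 0.3 | 5.5% | 9.5% |
| 0.5 | 3.9% | 6.8% |
| 0.7 | 2.4% | 4.1% |
| 0.9 | 0.8% | 1.4% |

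**3. Bias from selective loss.** Suppose return depends on D1. Among those who return, mean D1 is shifted by δR in the rhythmic-first order and by δA in the arrhythmic-first order. Mean D2 shifts by ρ times as much. The completer estimate is half the difference between orders in mean(D1 − D2), so

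bias = (1 − ρ)/2 × (δR − δA).

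It is zero whenever the two shifts are equal, because the selection then goes into the visit effect. The scenarios below use assumed loss rates. Those in tics also assume σ = 81 at both visits, carried over from the Aim 1 figure. For a cut-off that removes the worst fraction p of responders, δ = σφ(z)/(1 − p), where z is the normal quantile of p.

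- *No true difference, one common rule.* Losses are equal by order and the bias is 0.
- *True difference 41, common cut-off, 10% lost overall.* Losses are 5.8% rhythmic-first and 14.2% arrhythmic-first. The shifts are 81 × 0.122 = 9.9 and 81 × 0.263 = 21.3. Bias = (1 − ρ)/2 × (−11.4) = −4.0, −2.8, −1.7 tics at ρ = 0.3, 0.5, 0.7, so 41 becomes about 37 to 39.
- *Same rule, 27% lost overall (ceiling).* Losses are 18.8% and 35.2%, shifts 26.9 and 46.4. Bias = −6.8, −4.9, −2.9 tics, so 41 becomes about 34 to 38.
- *Smooth benefit-dependent rule, 19% v 28% lost, true effect 0.5 SD (simulated).* Bias is −0.026, −0.018, −0.012 SD at ρ = 0.3, 0.5, 0.7: a dilution of 5%, 4% and 2%. The standard error with 32 completers is √(2(1 − ρ)/32) = 0.21, 0.18, 0.14 SD, so the bias is about a tenth of a standard error.
- *Only one order loses its poor responders.* At 20% v 0%, δ = 81 × 0.350 = 28.3 and the bias is 9.9, 7.1, 4.3 tics. At 54% v 0%, δ = 81 × 0.863 = 69.9 and the bias is 24.5, 17.5, 10.5 tics. The sign depends on which order loses people.

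In simulation, an estimate that uses visit-1 data and models ρ recovered the true value within simulation error in each of these scenarios.

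**4. Which mixed model.** Random effects for participant and participant-by-visit both cancel from an on/off contrast. A model with only these forces ρ to zero. With no drop-out, its standard error for the three-way interaction is 1/√(1 − ρ) times the ANOVA's: 1.2, 1.4 and 1.8 at ρ = 0.3, 0.5, 0.7. Under the smooth rule above, its simulated bias is +0.013, +0.021 and +0.027 SD, so dilution becomes inflation. A participant-by-stimulation term is needed to carry ρ.

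**The case against.** The strongest case for the current rule is that little is at stake. One visit informs rhythmic versus arrhythmic only between persons, and response varies widely (SD about 81 around a mean of about 41). The planned 32 are completers, with enrolment up to 44. People judged unlikely to return are excluded, technical failures get a make-up session, and the larger payment comes at the second visit. The one withdrawal for discomfort that the plan foresees is at threshold testing; at visit 1 that precedes any stimulated block, so no model recovers those people. The analysis was registered before enrolment, and this is a pilot.

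Most of this stands. It makes the loss small and argues against displacing the registered test without thought. It does not answer the comparability point, because replacing drop-outs does not undo selection.

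A reader might infer that the exclusion necessarily biases Aim 2, or could manufacture a positive result. The documents do not support that. Under a common rule, bias requires a true difference, and it then works against the hypothesis. The large or inflating biases need loss confined largely to one order. Nothing in the documents points to that: both conditions use the same pulse count per minute at the thumb-movement threshold, and participants are blinded to order.

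**Conclusion.** The point holds as a modest improvement to the Aim 2 analysis, not as a fatal flaw. The completer-only rule discards usable visit-1 contrasts worth about 1% to 8% of the variance for six such participants (ρ from 0.9 to 0). It leaves the comparison open to bias if loss after visit 1 is selective and differs by order. With a true rhythmic advantage and a common tendency of non-benefiters not to return, the effect is diluted: 2% to 5% under the smooth rule, and up to 17% (6.8/41) under a sharp cut-off with the whole 27% lost after visit 1. With no true difference, the same rule gives no bias.

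These sizes rest on assumed values for ρ, for the number lost after visit 1 and for the drop-out rules. The 27% mixes screen failures with drop-outs, so the actual exposure may be much smaller.

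**What to change.** Fit a linear mixed model to all randomised participants with on/off data from at least one visit:

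- Fixed effects: visit, order, stimulation and all their interactions. Test the same three-way interaction.
- Random effects: participant, participant-by-visit and participant-by-stimulation, applied to one off mean and one on mean per visit. An unstructured covariance for the two per-visit on/off contrasts serves the same purpose. If single blocks are the rows, add participant-by-visit-by-stimulation so that block-to-block noise is not taken as the error for the contrast.
- Report it beside the registered two-visit completer ANOVA, and state in advance which is primary and which is the sensitivity analysis. Either order meets the concern.
- Report drop-out after visit 1 by session order, with reasons.

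The cost is small: a few extra videos to rate, and a wording change under Outcome measures, where analysis of a participant now starts only after the second visit. The model assumes that loss is missing at random given the observed data, which is weaker than the completer analysis needs but is still an assumption. Those who withdraw at threshold testing on visit 1 still contribute no on/off data.

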In June, 2020, [name]'s group at the University of Nottingham published a fascinating report in **Current Biology** on a potential novel treatment for tics [6]. The radical new idea arose from observations associating movement inhibition with 8-14 Hz activity in motor cortex. They first showed that rhythmic 12 Hz peripheral stimulation of the median nerve evoked synchronous contralateral EEG activity over primary sensorimotor cortex, whereas arrhythmic stimulation at the same mean rate did not. As hypothesized, median nerve stimulation (MNS) at 12 Hz created small but statistically significant effects on initiation of voluntary movements. Importantly, they also demonstrated that this stimulation did not meaningfully impair concentration, suggesting that the effect did not operate through simple distraction. They went on to test 10 Hz MNS in 19 TS patients, and demonstrated using blinded video ratings a significant reduction in tic number and severity during 1-minute stimulation epochs vs 1-minute no-stimulation epochs. They noted that in some participants, benefit lasted beyond the end of the stimulation epoch [*personal correspondence*]. Videos accompanying the publication showed dramatic benefit during MNS in some subjects. Although the authors appropriately noted the steps needed to generalize these results to clinical practice, news reports already have led a number of TS patients to contact them asking for treatment. The Nottingham group has referred such inquiries from the U.S. to me as leader of our Wash.U. Tourette Association of America (TAA) Center of Excellence.

We hypothesize that the tic benefits reported by our Nottingham colleagues are replicable, that they are specific to rhythmic stimulation, which alone entrained cortical activity, rather than to a placebo effect, and that they endure past the end of stimulation.

Here we propose (a) to replicate the Nottingham findings using identical methods, and (b) to test rhythmic MNS against a placebo treatment (arrhythmic MNS at the same mean frequency). At the same time, we will gather additional preliminary data needed for a future R01 application, including response and tolerability with longer (5-minute) stimulation blocks, and the duration of benefit after the end of a stimulation block.

Aim 1. Replicate the Nottingham MNS results in a new sample of people with TS. We have been in frequent contact with the Nottingham group to ensure that we can match their methods.

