2. Attach electrodes (so they're visible in the baseline video for optimal blinding).
3. Check resistance through electrodes. If $< 100 \Omega$, look for a short and correct it. If resistance remains out of range, do not proceed without specific approval from PI. Record resistance.
4. Optional but recommended bathroom stop
5. Procedures below are performed in a quiet room with only participant and study staff present but not conversing
6. All videos are recorded from the elbows up for later blinded ratings of tics
7. 5-min video-recorded baseline session, also rated live at the first visit to record baseline tic

frequency

8. At this point, the PI or designate will review the inclusion and exclusion criteria (including mean baseline tic frequency $\geq 1/\text{min.}$) and document eligibility for the study before additional procedures
9. Determine stimulation threshold for a train of 8 pulses (12 Hz, pulse width 200 μs), starting at 1mA and increasing until a twitch of the thumb is seen, to a maximum of 20mA (expected range 2-15 mA, *personal communication, [name] to [name]*). Some subjects may wish to withdraw at this point if suprathreshold stimulation is too uncomfortable, but in the Nottingham report, participants age 15 and up found the stimulation tolerable. Since electrode placement can change slightly between visits, on the second visit the threshold is verified and adjusted as needed. We record the threshold at each visit.
10. Resume video recording
11. Synchronize clocks for video, urge rating software, and stimulation
12. MNS stimulation on or off blocks as follows, without planned breaks (total 29-44 min.)
 - a. Two 1-min. blocks of MNS on and two 1-min. sessions off, the order of these 4 sessions randomized (*this design matches the Nottingham study*)
 - b. 5-min. block MNS off
 - c. 5-min. block MNS on
 - d. 5-min. block MNS off
 - e. 5-min. block MNS on
 - f. 5-minute stimulation **off** blocks until tics return to baseline frequency (min. 1 block, max. 4 blocks)
13. Stop video recording
14. CGI-I (Clinical Global Impression of Improvement) rating for tics by participant and investigator
15. Debrief
 - a. ratings of tic improvement and discomfort using the CGI Efficacy Index
 - b. ask for comments on benefit, tolerability, side effects
 - c. participant and staff guess whether this was active or control stimulation day (*to test adequacy of blinding*)
 - d. ask if they think they would use a portable stimulator

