- Square-wave 200 μ s pulses triggered by computer at the threshold for thumb movement (expected ~2-15mA) to surface electrodes over the median nerve at the right wrist (conductive gel, 30 mm apart center-to-center, anode distal)

ANALYSIS PLAN/APPROACH/METHODOLOGY

Outcome measures

The primary outcome measures are derived from audiovisual recordings (head to elbows), later broken into 1-min. or 5-min. clips, then rated in random order by an experienced movement disorders physician blind to stimulation conditions (on vs. off, rhythmic vs. arrhythmic) and order (rhythmic at first or second visit), who will record tic frequency and rate severity. For the 1-min. MNS on/off blocks, severity is rated on a 5-point scale (from the YGTSS severity item) for each occurrence of any tic, to replicate the methods of the Nottingham group. For the 5-min. blocks, overall tic severity is rated on the same scale once for each 5-min. block. This choice dramatically reduces rater time without sacrificing validity. Analysis for each participant can begin after his/her second stimulation visit is complete and all other data from that participant is checked.

Primary Outcome Measures:

1. Change in tic frequency compared to when MNS is off

An expert rater blind to condition and time point assesses the number of tics per minute. A one-tailed t test will compare mean tic frequency in the last 40 s of on vs. off 1-minute stimulation epochs on the rhythmic MNS day. This analysis replicates that of Study 3 in the Morera Maiquez et al 2020 citation. A secondary analysis will test for carryover effects.

[Time Frame: During rhythmic MNS stimulation]

2. Change in tic severity compared to when MNS is off

Severity is rated on a 5-point scale for each occurrence of any tic. The scale is the Intensity item from the Yale Global Tic Severity Scale [YGTSS], which uses integer scores from 0 (no tics) to 5 (severe intensity). A one-tailed t test will compare mean tic severity in the last 40 s of on vs. off 1-minute stimulation epochs on the rhythmic MNS day. This analysis replicates that of Study 3 in the Morera Maiquez et al 2020 citation. A secondary analysis will test for carryover effects.

[Time Frame: During rhythmic MNS stimulation]

3. Change in tic frequency during rhythmic MNS (vs. arrhythmic MNS)

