severity. The hypothesized change is a significant interaction of visit, order and stimulation factors ($p \leq .05$), showing greater improvement (off to on) with rhythmic *vs.* arrhythmic stimulation. The primary analysis will focus on the first six 5-minute blocks (*i.e.*, the ones that all participants complete). A secondary analysis examines the last 40 s of the four 1-minute blocks in the same way. Paired t tests will compare CGI-I ratings between stimulation conditions (rhythmic *vs.* arrhythmic).

Aim 2 interpretation: We chose arrhythmic stimulation as the control condition (“placebo”) because it did not increase stimulation-frequency EEG power in the sensorimotor cortex. However, we note that arrhythmic stimulation may itself possibly confer active benefit, which may produce a non-significant result for Aim 2. In that case a different control condition may be required for subsequent study, such as sub-motor-threshold stimulation current or a wait list condition. Additionally, this pilot study will not address the specificity of the stimulation site—as stimulation of another peripheral nerve may prove equally effective—nor the specificity of the 10-12 Hz stimulation frequency. Finally, other modifications may provide greater benefit; *e.g.* bilateral stimulation may be more effective than unilateral. All of these possibilities are reasonable goals of future study, but this pilot study focuses on the methods used in the published work.

Aim 3. The duration of benefit analysis will use a repeated measures ANOVA for tic scores from each 1-minute segment after the end of stimulation. A secondary approach may be to fit the tic scores from each participant after the end of each stimulation block to an exponential decay model. The analysis of individual characteristics that predict improvement with simulation will use a 2-tailed t test or correlation, as appropriate, for each measured demographic and clinical feature. These will include age, sex, baseline YGTSS, baseline OCD severity rating, baseline ADHD severity rating, history of complex tic(s), history of phonic tic(s), and motor and phonic tic frequency and severity at baseline (blinded ratings of the 5-minute block before stimulation on the first study visit). Other outcome variables, such as discomfort, adequacy of blinding, and interest in a portable stimulator, will be summarized descriptively.

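### Outcome 5 measures tics after stimulation against the stimulated level, so it cannot show how much benefit below the unstimulated level remains

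*Combined protocol and SAP*

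**What the plan says.** The Objectives section hypothesizes that the tic benefits are replicable, specific to rhythmic stimulation, "and that they endure past the end of stimulation". Aim 3(a) sets out to learn the duration of that effect and calls it crucial for designing chronic treatment.

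Secondary Outcome 5 is the analysis assigned to this. It is a repeated measures ANOVA on change in tic frequency from baseline for each minute after stimulation ends, with the definition "Here baseline means the tic frequency during the last 5 minutes of MNS from the same day". The Aim 3 paragraph under Data analysis repeats the ANOVA without naming a comparator. It adds that a second approach may be to "fit the tic scores from each participant after the end of each stimulation block to an exponential decay model".

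Elsewhere, baseline means an unstimulated level:
- Outcomes 3 and 4 gloss it as stimulation off.
- Step 7 of the Stimulation protocol is a "5-min video-recorded baseline session", made before any stimulation.
- The Aim 3 predictor analysis uses "blinded ratings of the 5-minute block before stimulation on the first study visit".
- Step 12f continues off blocks (one to four, 5 minutes each) until tics are back at baseline frequency, which makes sense only for an unstimulated level.

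**The concern.** Benefit is a reduction below the unstimulated tic rate. An analysis of how long benefit lasts must say how far below that rate tics still are at each time after stimulation. Outcome 5 says how far tics have risen above the stimulated rate, which is a different quantity. A flat result could mean that nothing wore off or that there was nothing to wear off.

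If the hypothesis of enduring benefit were fully true, the planned contrast would be expected to be null, just as for an inert treatment. The duration information wanted for the next trial could then be misread in either direction.

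Two smaller features of the same outcome add to the difficulty. Follow-up runs 5 to 20 minutes depending on the participant's own tic rate, and Outcome 5 is not restricted to minutes that everyone completes. The title also says severity while the method uses frequency; each 5-minute block gets only one severity rating, so a minute-by-minute severity analysis is not available.

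**Working it through.** The plan states no power or sample size for Outcome 5, so there is no figure to reproduce. The check is on what the contrast identifies.

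**Algebra.** Let *off*, *on* and *post(t)* be the mean tic rates unstimulated, in the last 5 minutes of MNS, and at time *t* afterwards.
- Outcome 5: D(t) = post(t) − on.
- Remaining benefit: R(t) = off − post(t) = (off − on) − D(t).

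D(t) does not contain *off*, so it does not determine R(t).

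**Expected values.** Set off = 100 and on = 70 (the roughly 30% decrease in Power considerations), with no session drift. The inert case has on = 100. The 5-minute half-life is assumed; its mean benefit over minutes 0-5 is 30 × 0.5/ln 2 = 21.6.

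| Case, mean of post-MNS minutes 1-5 | post | vs MNS-on (plan) | vs off |
|---|---|---|---|
| MNS inert | 100 | 0 | 0 |
| Benefit fully persists | 70 | 0 | −30 |
| Benefit halves every 5 min | 78.4 | +8.4 | −21.6 |
| Benefit lost at once | 100 | +30 | 0 |

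The ambiguity is not confined to zero. D = +15 fits on 85/post 100 (nothing retained), on 70/post 85 (half retained) and on 40/post 55 (45/60 = 75% retained).

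**Whether other planned analyses fill the gap.**
- *Decay fit.* It is optional, names no off-level asymptote, and cannot interpret a flat series.
- *Carryover.* Under Outcomes 1 and 2 the plan says "A secondary analysis will test for carryover effects", but those outcomes concern the 1-minute epochs.
- *Outcome 3.* It uses six 5-minute blocks that everyone completes. Step 12 supplies five: 12b, 12c, 12d, 12e and the first 12f block. Its stated 29-44 minutes equals 4×1 + 4×5 = 24 plus 5-20, so the pre-stimulation block lies outside step 12 and must be the sixth. The off blocks are then pre, 12b, 12d and the first 12f block, two of which follow a 5-minute MNS block. With full persistence, the off mean is (100+100+70+70)/4 = 85 and the within-day on-minus-off contrast is 70 − 85 = −15. If the 1-minute MNS blocks have already lowered 12b, the off mean is 77.5 and the contrast −7.5. If benefit is lost at once, it is −30. Outcome 3 therefore shows least when benefit persists most.

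**Precision of an off-referenced contrast.** Power considerations "shows the SD of the improvement in tic frequency between the MNS on and off conditions to be ~81", with a mean difference of about 41. As a share of the off rate, SD = 81/41 × 30% = 59%. With n = 32 the standard error is 59.3/√32 = 10.5, and the 95% half-width is 2.04 × 10.5 = 21.4%. Two-sided paired-t power is 79% for −30, 51% for −21.5 and 28% for −15. That SD comes from 1-minute epochs. If it were 40% or 30% (assumed), the half-width would be 14.4% or 10.8%.

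**Drift.** With inert MNS, suppose the rate falls by an assumed 5% or 10% between the pre-stimulation block and minutes 1-5. A two-sided 5% test would then declare a false reduction in 7% or 15% of trials at SD 59%, and in 15% or 45% at SD 30%.

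**The case against.** The strongest reply is that Outcome 5 is not read alone. Outcome 1 compares on with off on the same rhythmic day, and Outcome 3 uses the 5-minute blocks, so an inert treatment and a fully persistent one would look different there. This is partly right. Under full persistence Outcome 1 still has a nonzero expectation: an off minute precedes both on minutes with probability 1/3, so the off mean is 100/3 + 70×2/3 = 80 and the contrast is −10. Outcome 3 gives −15 or −7.5 within the day, and its rhythmic-versus-arrhythmic test sees that amount only if arrhythmic MNS is inert. These analyses separate the two cases weakly, and none measures what remains after stimulation.

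Three further points have merit:
- The MNS-on reference is an explicit local definition. It gives a legitimate loss-of-effect contrast, and because the reference block immediately precedes follow-up, it is the least exposed to drift. That is a reason to keep it alongside an off-referenced contrast.
- Complete persistence is a limiting case. The hypothesis says that benefit endures, not that it is undiminished, and with a 5-minute half-life the planned contrast is +8.4, not 0. But the +15 example shows that a nonzero rise does not reveal what remains either.
- Step 12f yields a crude duration in 5-minute steps. No analysis of it is specified.

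The pre-stimulation block is not a perfect reference. It is separated from follow-up by 24 minutes of blocks, and at visit 1 it is also the block used for eligibility, so regression to the mean is possible. The fix has to carry checks for this.

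**Conclusion.** The concern holds. Outcome 5 does not measure the quantity it is introduced to estimate. Its expected value is 0 both for inert MNS and for a fully persistent benefit, whereas an off-referenced contrast would differ by 30% of the off rate between those two cases. This rests on the protocol's 30% effect and on no session drift; the algebraic point does not depend on the size of the effect.

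The fault lies in the definition of the contrast, because the blocks needed are already recorded and rated. It should be fixed, with importance in proportion: this is a secondary outcome of a pilot, the plan itself treats Aim 3 as mainly hypothesis-generating, and no primary conclusion is affected.

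**What to change.** In Outcome 5 and the matching Aim 3 paragraph:

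1. Define remaining benefit as the reduction in tic frequency below a same-day stimulation-off level. Use the pre-stimulation 5-minute block as reference and the step 12b off block as a sensitivity reference. 12b is closer in time (15 minutes from its end to follow-up) but may carry over from the 1-minute MNS blocks.
2. Report it per minute with 95% confidence intervals for the rhythmic day, with the arrhythmic day beside it as a check on drift. Note the plan's own caution that "arrhythmic stimulation may itself possibly confer active benefit". The per-minute report matters because one mean can hide the shape: a 30% benefit for 2.5 minutes and a 15% benefit throughout both average −15, but give −30, −30, −15, 0, 0 and −15 in every minute.
3. Base formal inference on the mean of post-MNS minutes 1-5, which all participants complete. State that this tests whether benefit remains and does not by itself estimate its full duration.
4. Show minutes 6-20 descriptively with the number observed, because continuation depends on the participant's own tic rate.
5. Keep change from the MNS-on level as a descriptive decay curve. If the exponential model is fitted, use the off level as its asymptote.
6. Retitle the outcome as tic frequency, and use different words for the two reference levels.

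The cost is a few sentences. No new recordings are needed: the pre-stimulation, 12b and first post-MNS blocks are among the six already rated on each day. The price is a shorter window for formal inference, the modest precision shown above, and sensitivity to drift, which the 12b and arrhythmic-day checks expose but do not remove.
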